## Correction for drop-out

We expect that a proportion of the participants will already have SARS-CoV-2 antibodies at baseline and will not be evaluable for the primary endpoint. In addition, we anticipate that there will be a drop-out of participants at later time points. Reasons for drop-out may include death or poor performance status as a result of progressive malignancy and/or cancer treatment related AEs. Therefore, we will correct for non-evaluable patients by increasing each cohort with 20%. This means that 246 participants will be recruited in cohorts A, C and D, and 135 participants will be enrolled in cohort B. In total, 873 participants (627 patients and 246 individuals without cancer) will be included.

#### 5. TREATMENT OF SUBJECTS

Vaccination will be performed according to the standard of care. The name of the vaccine, batch number and date and time of administration will be recorded. This study investigates the immune response and AEs in a vulnerable population of patients who receive cancer treatment. If subjects had not participated in this study, they would have received the same vaccine or another registered vaccine against COVID-19 according to standard of care via their general practitioner without additional testing.

# 6. INVESTIGATIONAL PRODUCT

The product information of the approved mRNA-1273 SARS-CoV-2 vaccine administered to participants in this study is provided in Appendix 4.

## 7. NON-INVESTIGATIONAL PRODUCT

Not applicable

#### 8. METHODS

#### 8.1 Study parameters/endpoints

#### 8.1.1 Main study parameter/endpoint

The primary endpoint is the antibody based immune response to vaccination against COVID-19 on day 28 after the second vaccination in patients receiving cancer treatment as compared to individuals without cancer. Participants will be classified as responders or non-responders. The definition of response is seroconversion defined as presence of SARS-CoV-2 spike S1-specific IgG antibodies in individuals without measurable anti-S antibodies at baseline. Participants who are seropositive at baseline will not be included in the analysis of the primary endpoint (see paragraph 10.1). The percentage of responders of each patient cohort will be compared with the percentage responders in the group without cancer.

#### 8.1.2 Secondary study parameters/endpoints

- Safety assessment through:
  - Incidence and severity of solicited AEs during 7 days after each vaccination (see Appendix 1)
  - o Incidence and nature of SAEs during 7 days after each vaccination
  - Incidence and nature of newly occurring irAEs [38] grade ≥ 3 in cohort B and D up to 28 days after the last vaccination graded according to the Common Terminology Criteria for Adverse Events version 5.0 (CTCAEv5.0)
  - Incidence, nature and severity of AESIs (see Appendix 2) graded according to CTCAEv5.0
- In depth assessment of immune response through:

- Measurement of SARS-CoV2 specific antibodies before the second vaccination to analyze initial response, and at 6 and 11 and 18 months after the second vaccination to measure longevity
- Measurement of SARS-CoV2 specific antibodies at day 28 after the third vaccination if applicable
- Assessment of SARS-CoV2 specific T cells response at 28 days after the second and third vaccination and at 6, 11 and 18 months after the second vaccination using a high throughput Interferon y ELIspot

# 8.1.3 Exploratory study parameters

- In-depth flow-cytometric analyses for functional and phenotypical characterization of SARS-CoV-2 specific cellular immune responses will be performed followed by assessment of proliferative capacity, cytokine production and phenotypical markers in a subset of patients
- To determine baseline (immune) parameters associated with immune response to COVID-19 vaccination
- To assess the induction of SARS-CoV-2-specific antibodies in mucosal lining fluid
- Neutralizing capacity of antibodies to test functionality.
- Information on incidence of SARS-CoV-2 infection, outcome of COVID-19 will be collected and reported during 18 months after the second vaccination. To this end, questionnaires will be used. Information on positive corona tests during the study will also be collected from the RIVM.
- To analyze SARS-CoV-2-binding antibody concentration after a third vaccination in participants without an adequate antibody response after two vaccinations on day 28 after the third vaccination.
- To analyze safety of a third vaccination as indicated under 8.1.2
- To assess SARS-CoV2 specific T cell response at 28 days after the third vaccination

# 8.2 Randomization, blinding and treatment allocation

Not applicable.

# 8.3 Study procedures

This study is executed as a low-risk intervention trial, for which no labeling is required according to Annex 13. However, the vaccine release and drug accountability will be done according to GCP.

## Table 1: Flow chart/time and events schedule

Procedure	Screening a	Vacc	Vacc	Day	Day	Day	Vacc	Day	Day	Day	Day
	(within 28	1	2	28	90	180	3 m	28	270	330	540 (±
	days)			vacc	(±7)	(± 7)		vacc	(±7)	(± 14)	21)
				2 b				3			
				(± 3)				(± 3)			
Informed consent	х						х				
Inclusion/exclusion											
criteria	x										
Medical history	х										
Concomitant											
medication	x	х	х	х		X	x	х		x	X
Smoking history	х										
ECOG PS b	х										
Height/weight	х						х				
Vital signs c	х	х	х				х				
Blood tests d		х	х	х		х	х	х		х	х
Nasal MLF				х							
collection e		X									
Sollicited adverse				х							
events f	X	X	X				X				
SAEs g		х	х	х			x				
irAEs h	х	х	х	х			х	х			
AESIs i			Will be	e report	ed for t	he entii	re durat	ion of th	ne study		
Vaccine		~	~								
administration j		X	X				X				
COVID-19					~	~					
questionnaire k	X				X	X	X		x	x	x
Survival status						х				x	x

a Screening should be performed within 28 days prior to the first vaccination but can be done on the same day as the first vaccination.

b ECOG performance status: see appendix 3.

c Vital signs: blood pressure, heart rate, temperature.

d See Table 2.

e MLF = mucosal lining fluid, will be collected using a synthetic absorptive matrix [39] f Participants will complete a questionnaire for solicited systemic and local AEs on a daily basis from each vaccination until 7 days after each vaccination, see Appendix 1. g SAEs that occur within 7 days of each vaccination will be reported

h Newly developed irAEs [38] grade  $\geq$  3 need to be reported for cohort B and D up to 28 days after the second vaccination and from the third vaccination to 28 days thereafter.

i AESIs (see Appendix 2) will be reported by the treating physicians up to 18 months after vaccination for cohorts B-D.

j The name of the vaccine, batch number and date and time of administration will be recorded.

k Participants will complete a questionnaire for diagnosis of SARS-CoV-2 infection, severity and outcome of COVID-19.

 Only participants with an inadequate antibody response (≤300 BAU/mL) on day 28 after the second vaccination.

	Vacc1 a	Vacc2 a	Day	Day		Day		Day
			28	180	Vacc3 ad	28	Day	540
			Vacc2			vacc3	330	
SARS-Cov-2	х	х	х	х	х	х	х	х
antibodies								
PBMC isolation	х		х	х	х	х	х	х
for in depth								
cellular								
immune								
response								
Routine	х	х	х	х	х	х	х	х
hematology b								
Routine	х	х	х		х	х		
chemistry c								

Table 2: Blood tests

PBMC = peripheral blood mononuclear cells

a Blood has to be drawn before vaccination

b Hemoglobin, red blood cell count, platelet count, white blood cell count, white blood cell differential

c glucose, creatinine, aspartate aminotransferase (ASAT), alanine aminotransferase (ALAT), albumin, lactate dehydrogenase (LDH), C-reactive protein (CRP).

d Only participants with an inadequate antibody response (≤300BAU/mL) on day 28 after the second vaccination.

# 8.4 Withdrawal of individual subjects

Subjects can leave the study at any time for any reason if they wish to do so without any consequences. The investigator can decide to withdraw a subject from the study for urgent medical reasons.

#### 8.4.1 Specific criteria for withdrawal (if applicable)

Not applicable

## 8.5 Replacement of individual subjects after withdrawal

Not applicable

## 8.6 Follow-up of subjects withdrawn from treatment

Participants who receive at least one dose of the vaccine will be monitored for AEs, SAEs, AESIs and irAEs according to the protocol (up to day 7 after each vaccination for cohorts A and C and up to day 28 after the last vaccination for cohorts B and D). If the subject does not withdraw consent, also blood samples will be drawn according to the protocol.

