To evaluate vaccination related AEs, patients will be asked to collect solicited local and systemic AEs for 7 days after each vaccination using a questionnaire. Similarly serious AEs (SAEs) will be collected for 7 days after each vaccination. Most patients who receive systemic cancer treatment experience multiple AEs that are cancer treatment related, or disease related. As vaccination related AEs are mainly expected within the first week after vaccination, it is not useful to collect all AEs for a prolonged period. Instead, all newly occurring immune related AEs (irAEs) are collected for the immunotherapy and chemo-immunotherapy cohorts (B and D) up to 28 days after the second and if applicable the third vaccination. irAEs are toxicities from immune checkpoint inhibitors and do not include infusion reactions [38]. Furthermore, adverse events of special interest (AESIs) will be collected for the duration of the study in the patient cohorts.

Information on incidence of SARS-CoV-2 infection, outcome of COVID-19 during 18 months after the second vaccination will be collected using questionnaires. For the study participants who give separate consent, information on positive corona tests during the study will also be collected from the RIVM.

Although this study is not powered to detect differences in protection against COVID-19 between patients and controls, information on incidence of SARS-CoV-2 infection, outcome of COVID-19 will be collected up to 18 months after the second vaccination for descriptive purposes.

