# 9.2.3 Adverse events of special interest (AESIs)

Adverse events of special interest (AESIs) and serious adverse events (SAEs) frequently occur in patients with cancer who receive systemic therapy as a result of the cancer treatment or the underlying disease. Therefore, AESIs will be collected in this study (see Appendix 2). Treating physicians from patients in cohorts B, C and D will report AESIs to the PI. The coordinating investigator, the PI or delegated trial personnel will report the AESIs through the web portal ToetsingOnline to the accredited METC that approved the protocol, within 15 days after first knowledge of the AESIs.

Since the vaccine is a registered agent, and the number of controls in this study is very small compared to the registration trials, AESIs from the control group will not meaningfully add to the existing safety data. Therefore, subjects in the control group will be asked to report potential side effects of vaccination according to the national guidelines for the general population to the Dutch pharmacovigilance center Lareb.

Death of any cause is considered an AESI, because life expectancy of at least 12 months is required for inclusion. We will report deaths and collect information on cause of death. In order to be as complete as possible, informed consent is asked for coupling of data with the Gemeentelijke Basis Administratie (GBA) and Centraal bureaus voor Statistiek (CBS), also from individuals without cancer. However, this is optional and participants who do not consent to coupling of data with CBS and GBA can participate in the study.

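### Section 8.6 lists AESIs under a day-7/day-28 window that contradicts the 18-month AESI rule for cohorts B-D; probably merged shorthand, but worth a one-sentence correction

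*Combined protocol and SAP*

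**What the plan says.** Section 8.6 covers anyone who has had at least one dose. Such participants "will be monitored for AEs, SAEs, AESIs and irAEs according to the protocol", and a bracket follows with the time limits: "up to day 7 after each vaccination for cohorts A and C and up to day 28 after the last vaccination" (the latter limit in B and D). All four event types stand in front of that one bracket.

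The event-specific rules are elsewhere:

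- **AESIs.** Section 3 says that "adverse events of special interest (AESIs) will be collected for the duration of the study in the patient cohorts". The AESI row of Table 1 spans the entire study, and footnote i says that AESIs "will be reported by the treating physicians up to 18 months after vaccination for cohorts B-D". Section 9.2.3 gives the route: "Treating physicians from patients in cohorts B, C and D will report AESIs to the PI". Controls report suspected side effects through the national pharmacovigilance centre instead.
- **SAEs.** Table 1 footnote g: "SAEs that occur within 7 days of each vaccination will be reported". This applies to all cohorts.
- **irAEs.** These are collected in B and D only. Sections 8.1.2 and 9.2.4 run to 28 days after the last vaccination. Table 1 footnote h words the period as "up to 28 days after the second vaccination and from the third vaccination to 28 days thereafter".

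AESIs are a named secondary safety endpoint in section 8.1.2: "Incidence, nature and severity of AESIs (see Appendix 2) graded according to CTCAEv5.0". Section 10 keeps everyone with at least one administration in the AESI analysis, and section 10.2 lists AESI numbers and frequencies per cohort and by severity.

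**The concern.** Section 8.6 restates the monitoring rules and gets the AESI rule wrong. No text takes AESIs out of the bracket. A site with a patient who has stopped vaccination would naturally look in 8.6, and could take the specific section as governing.

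If it did, AESI reporting for that patient would end after 7 or 28 days, and a late non-fatal AESI could be missed. The patient would still be counted in the AESI analysis beside patients observed for about 18 months, and the listing would not show the difference. The monitor also checks for missed AESIs (section 12.2), and two windows leave no single standard for what counts as missed.

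**Working it through.** This is a comparison of texts; there is no sample size, power or error-rate figure to reproduce.

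**Step 1: the bracket against the event-specific rules.**

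| Event | Rule elsewhere | Section 8.6 read literally | Result |
|---|---|---|---|
| Solicited AEs, SAEs; A and C | 7 days after each dose (8.1.2; Table 1 footnotes f, g) | 7 days after each dose | Agree |
| Solicited AEs, SAEs; B and D | 7 days after each dose (same) | 28 days after the last dose | Differ |
| irAEs; B and D | 28 days after the last dose (8.1.2, 9.2.4) | 28 days after the last dose | Agree |
| irAEs; A and C | Not collected | 7 days | Cannot apply |
| AESIs; C | Up to 18 months (section 3; footnote i) | 7 days after each dose | Contradict |
| AESIs; B and D | Up to 18 months (same) | 28 days after the last dose | Contradict |
| AESIs; A | Not collected by the study; national route (9.2.3) | 7 days | Does not fit |

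The day-7 figure matches the solicited AE and SAE rule, and the day-28 figure in B and D matches the irAE rule. No other section gives AESIs either window. This pattern is what merging two rules into one bracket would produce.

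**Step 2: size of the discrepancy for one patient.** Take 18 months as day 540, as in Table 1, counted from the last dose received.

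- Cohort C: 7/540 = 1.3% of the window is kept, and 540 − 7 = 533 days fall outside the bracket.
- Cohorts B and D: 28/540 = 5.2% is kept, and 540 − 28 = 512 days fall outside.

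**Step 3: how many patients.** The documents do not say how many stopped after dose 1. Section 1.6 gives 791 enrolled and 743 evaluable for the primary endpoint (check: 240 + 131 + 229 + 143 = 743). So 791 − 743 = 48 were not evaluable, and 48/791 = 6.1%.

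If the per-protocol set required both doses (an assumption), the number of dose-1 stoppers lies between 0 and 48. This is a loose ceiling. The 48 include controls, and may include participants seropositive at baseline, whom sections 4.4 and 8.1.1 expect and exclude, as well as deaths and missed day-28 samples. The number in B-D is smaller still and could be zero. Missed events cannot be computed.

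**Step 4: what would still be captured.** Deaths are AESIs, but they are covered separately by the survival-status row of Table 1 (days 180, 330 and 540) and by optional registry linkage (9.2.3). The study contacts on those days include blood tests and concomitant medication. They might bring another event to light, but they are not AESI checks. Section 9.4 follows known events to resolution or stability and does not extend detection. What remains exposed is late non-fatal AESIs.

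**The case against.** The strongest reply is that the protocol already holds the right rule. Section 8.6 defers to the protocol in its own sentence, and Table 1, footnote i and section 3 are unambiguous. The bracket cannot be a literal rule for every event it names, since irAEs do not apply in A and C and the study does not collect AESIs from controls. AESIs reach the PI through treating physicians, a route that does not depend on visits or on dose 2. On this view a site has little reason to prefer the bracket.

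Timing also limits the benefit. Enrolment ended in March 2021 and this version plans measurements for 2022 (sections 1.6 and 1.8), so any dose-1 stopper is long past day 28. A correction helps only the AESI follow-up that remains.

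Most of this stands, and it is why the point is minor. It does not make the sentence correct: 8.6 names AESIs, gives them a window, and that window is wrong.

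A reader might go further and infer one of three things that the documents do not support:

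- **That the plan deliberately shortens AESI follow-up for patients who stop vaccination.** No text says so, and the misfit for SAEs and irAEs points to shorthand rather than choice.
- **That AESI data were lost, in up to 48 patients.** Nothing shows that any site followed the bracket, and the 48 are not a count of dose-1 stoppers.
- **That deaths would go unrecorded or the primary result would change.** Deaths have their own capture, although registry linkage is optional, and the primary endpoint does not use AESI data.

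**Conclusion.** The inconsistency is certain on the text: 7 days (C) or 28 days (B, D) in section 8.6 against about 540 days elsewhere for AESIs, and 28 against 7 days for SAEs in B and D. The consequence is conditional. If sites follow Table 1, nothing is lost. If a site follows the bracket, late non-fatal AESIs go unreported in a patient who stops vaccination, and that patient still counts in the AESI analysis. The number affected is unknown, and only the descriptive listing in section 10.2 is exposed. This is an internal inconsistency of low severity, worth correcting because it concerns a named secondary safety endpoint and costs almost nothing.

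**What to change.** Either delete the bracket in section 8.6 and let the reference to the protocol stand, or split it by event type for everyone with at least one dose, whether or not the series is completed:

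- Solicited AEs and SAEs: 7 days after each vaccination received, all cohorts.
- irAEs: cohorts B and D, to 28 days after the last vaccination received, as in 8.1.2 and 9.2.4. Those sections are preferred to footnote h because, with a third dose, footnote h leaves out the time from day 28 after dose 2 to dose 3.
- AESIs: cohorts B-D, up to 18 months after vaccination as in Table 1 footnote i, counted from the last primary dose received if dose 2 is not given.

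The split is preferable because footnote i names no dose, so deleting the bracket leaves the starting point unstated for a patient who never receives dose 2. That starting point is the only new rule; every other window is already in the protocol. Cohort A keeps the national reporting route for non-fatal events, and the capture of deaths is unchanged. The cost is one reworded sentence, with no added visit, sample or analysis.

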## 8.7 Premature termination of the study

Not applicable since vaccination is standard of care.

## 9. SAFETY REPORTING

## 9.1 Temporary halt for reasons of subject safety

In accordance to section 10, subsection 4, of the WMO, the sponsor will suspend the study if there is sufficient ground that continuation of the study will jeopardize subject health or safety. The sponsor will notify the accredited METC without undue delay of a temporary halt including the reason for such an action. The study will be suspended pending a further positive decision by the accredited METC. The investigator will take care that all subjects are kept informed.

# 9.2 AEs, AESIs and SUSARs

#### 9.2.1 Adverse events (AEs)

AEs are defined as any undesirable experience occurring to a subject during the study, whether or not considered related to COVID-19 vaccination. In this study, solicited AEs will be reported by all participants on a daily basis for 7 days after each vaccination.

# 9.2.2 Serious Adverse events (AEs)

A serious adverse event is any untoward medical occurrence or effect that

- results in death;

- is life threatening (at the time of the event);
- requires hospitalisation or prolongation of existing inpatients' hospitalisation;
- results in persistent or significant disability or incapacity;
- is a congenital anomaly or birth defect; or
- any other important medical event that did not result in any of the outcomes listed above due to medical or surgical intervention but could have been based upon appropriate judgement by the investigator.

An elective hospital admission will not be considered as a serious adverse event.

The investigator will report all SAEs that occur within 7 days of administration of the vaccine to the PI without undue delay after obtaining knowledge of the events.

The coordinating investigator, the PI or delegated trial personnel will report the SAEs through the web portal ToetsingOnline to the accredited METC that approved the protocol, within 7 days of first knowledge for SAEs that result in death or are life threatening followed by a period of maximum of 8 days to complete the initial preliminary report. All other SAEs will be reported within a period of maximum 15 days after the sponsor has first knowledge of the serious adverse events.

# 9.2.3 Adverse events of special interest (AESIs)

Adverse events of special interest (AESIs) and serious adverse events (SAEs) frequently occur in patients with cancer who receive systemic therapy as a result of the cancer treatment or the underlying disease. Therefore, AESIs will be collected in this study (see Appendix 2). Treating physicians from patients in cohorts B, C and D will report AESIs to the PI. The coordinating investigator, the PI or delegated trial personnel will report the AESIs through the web portal ToetsingOnline to the accredited METC that approved the protocol, within 15 days after first knowledge of the AESIs.

Since the vaccine is a registered agent, and the number of controls in this study is very small compared to the registration trials, AESIs from the control group will not meaningfully add to the existing safety data. Therefore, subjects in the control group will be asked to report potential side effects of vaccination according to the national guidelines for the general population to the Dutch pharmacovigilance center Lareb.

Death of any cause is considered an AESI, because life expectancy of at least 12 months is required for inclusion. We will report deaths and collect information on cause of death. In order to be as complete as possible, informed consent is asked for coupling of data with the Gemeentelijke Basis Administratie (GBA) and Centraal bureaus voor Statistiek (CBS), also from individuals without cancer. However, this is optional and participants who do not consent to coupling of data with CBS and GBA can participate in the study.

